## Introduction

The following Statistical Analysis Plan (SAP) describes the planned analysis and data presentations for "Cannabidiol Effects on Craving and Relapse Prevention in Opioid Use Disorder", protocol version dated 08 June 2023. Changes to the protocol may result in subsequent changes to the SAP.

The purpose of the SAP is to ensure the credibility of the study findings by pre-specifying the statistical approaches to the primary and secondary RCT data analyses prior to database lock. This SAP will be finalized and signed prior to the clinical database lock for the final analysis. Any significant changes after the final database lock will be documented in a final SAP Amendment. All statistical analyses detailed in this plan will be conducted using SAS® 9.4 or a later version.

The planned analyses identified in this SAP may be included in clinical study reports (CSRs), regulatory submissions, or future manuscripts. Also, post hoc exploratory analyses not necessarily identified in this SAP may be performed to examine study data further. Any post hoc, or unplanned, exploratory analyses performed will be clearly identified as such in the final CSR.

## 1. Glossary of Abbreviations

AE	Adverse Event
2-AG	2-Arachidonoylglycerol
ALT	Alanine transaminase
AST	Aspartate transaminase
Bup	Buprenorphine
CBD	Cannabidiol
ConMeds	Concomitant medications
COWS	Clinical Opiate Withdrawal Scale
CRF	Case report form
C-SSRS	Columbia Suicide Severity Rating Scale
CYP3A	Cytochrome P450, family 3, subfamily A
DDQ	Desires for Drug Questionnaire
DSMB	Data safety monitoring board
EDDP	2-ethylidene-1, 5-dimethyl-3, 3-diphenylpyrrolidine
EKG	Electrocardiogram
FDA	Food and Drug Administration
FSH	Follicle-stimulating hormone
HIV	Human immunodeficiency virus
Hg	Mercury
HR	Heart rate
IMP	Investigational medicinal product
InfCons/Demogr	Informed consent/demographics
LH	Luteinizing hormone
MedDRA	Medical Dictionary for Regulatory Activities
MedHx/PsychHx	Medical history and psychiatric evaluation
MFA	Multi-factor authentication
MINI	Mini International Neuropsychiatric Interview 7.0.2 for DSM-5
NorBup	Norbuprenorphine
OAAS	Observed Observer's Assessment of Alertness/Sedation Scale

OUD	Opioid use disorder
PACS	Penn Alcohol-Craving Scale adapted for opioid craving
PANAS	Positive and Negative Affect Schedule
PI	Principal investigator
PK	Pharmacokinetic
PO	Per os (orally)
QRS	Combination of the Q, R and S waves (QRS complex), representing ventricular
QT	Time from the start of the Q wave to the end of the T wave on EKG
QTc	Corrected QT interval
SAP	Statistical analysis plan
SOC	System organ class according to the MedDRA dictionary
SOP	Standard operating procedure
STAI	Spielberger State-Trait Anxiety Inventory
T3	Triiodothyronine
T4	Thyroxine
TBG	Thyroxine-binding globulin
THC	Tetrahydrocannabinol
THS	Thyroid-stimulating hormone
ULN	Upper limit of normal

## 2. Background

Opioid Use Disorder (OUD) is a public health emergency leading to unprecedented drug-related mortality in the United States, underscoring the need for innovative medical treatments. Three medications are FDA-approved for treatment of OUD, but retention in treatment is low even with medication. Positive findings from preclinical and clinical studies provide a rationale for the use of cannabidiol (CBD) in treatment of OUD. Notably, a Phase 2, randomized, double-blind, placebo-controlled, pilot study found that a single dose of CBD (400 or 800 mg) decreased cue-induced opioid craving and blunted anxiety. Still, rigorous clinical trials are needed to establish the value of CBD as adjunctive therapy for OUD.

Based on prior work, CBD is expected to be well-tolerated and safe in patients with OUD, but safety signals (vital signs and laboratory test results) will be assessed in more detail here. Specifically, because CBD inhibits cytochrome P450 isozymes including CYP3A, the primary mechanism for hepatic buprenorphine N-dealkylation, we will evaluate whether CBD poses potential safety concerns associated with buprenorphine treatment. Specifically, we will seek to evaluate the frequency and magnitude of this possible drug-drug interaction to ensure safe and effective treatment of OUD for patients receiving medication-assisted treatment with buprenorphine. In addition to assessing safety, this study will provide preliminary information on the efficacy of CBD compared with matched placebo as an adjunctive treatment in patients receiving medication-assisted treatment for OUD.

Beyond the safety and efficacy objectives, prior research indicated that CBD increases fatty acid amide hydrolase, the principal enzyme catalyzing catabolism of the major endocannabinoids anandamide and 2-AG. More recent work, however, indicates that CBD inhibits anandamide uptake into cells. As such, CBD administration may affect plasma concentrations of these endocannabinoids. Plasma levels of anandamide and 2-AG will be assayed to explore whether CBD increases their concentrations in this study.

### 3. Study Overview

#### 3.1. Study Design, Blinding, and Randomization

This is a randomized, double-blind, placebo-controlled, phase 2 trial to evaluate the safety and efficacy of CBD as adjunctive therapy in patients receiving medication-assisted inpatient treatment for OUD. It is a single-site study, conducted at a residential treatment center. The original plan was for ~60 subjects to be randomized (2:1 CBD:placebo) for study in two ascending dose cohorts, the first receiving CBD 600 mg/day orally (PO) (n = 20) or placebo (n = 10) and the second receiving CBD 1200 mg/day PO (n = 20) or placebo (n = 10), ultimately creating three equal arms. Due to budgetary constraints, the higher-dose cohort was eliminated, and the randomization ratio was reversed to 2:1 placebo: CBD 600 mg/day towards the end of the lower-dose segment of the study to balance the remaining two arms as much as possible. This SAP is based on data from 28 participants randomized using a 2:1 CBD 600 mg/placebo ratio and 7 participants randomized using a 2:1 placebo:CBD 600 mg ratio.

**Study Periods:** The study design comprised four phases: 1) a 14-day screening period during which patients were consented, evaluated against entry criteria, and stabilized on buprenorphine; 2) randomization and baseline evaluation (Day 0); 3) a 28-day acute treatment period when each participant received the IMP twice daily (CBD or placebo); primary data collection phase, and 4) a 28-day follow-up period after termination of treatment with study medication (secondary data collection phase). Safety assessments included clinical lab tests during screening and weekly during the treatment and follow-up periods. On each study day, vital signs were taken, and patients reported adverse events, which were monitored and recorded. Although not a direct measure of safety, change in buprenorphine metabolism, operationalized as the ratio of buprenorphine to norbuprenorphine in plasma, was obtained, as out of range values occurring in the context of hypoxia and/or sedation could be indicative of increased risk. Because CBD inhibits CYP3A, the primary mechanism for hepatic buprenorphine N-dealkylation, the buprenorphine to norbuprenorphine ratio was measured in blood drawn for relevant PK analyses at baseline and weekly during the treatment and follow-up periods. Cue-induced craving was measured in laboratory sessions with a paradigm in which neutral and opioid-related cues were presented. These sessions were conducted before dosing on Day 0 (Baseline) and on Days 7 and 28 after study drug initiation (Treatment Phase).

The original protocol was approved by the FDA on October 12, 2020 (IND 152888). Modifications were needed because the approved investigational product became unavailable. On October 27, 2021, the FDA approved using ATL5 (100 mg/ml CBD softgel capsules) and matching placebo as the investigational medicinal products (IMPs), and testing two ascending-dose cohorts [cohort 1: CBD 600 mg/day, N = 20 and placebo (N = 10); cohort 2: CBD 1200 mg/day, N = 20 and placebo, N = 10)], each randomized 2:1 CBD:placebo, with the combined placebo subsamples intended to be treated as a common reference for both drug groups. The trial commenced in March 2022.

[figure not shown]
Randomization was stratified by baseline (i.e. post-stabilization period) plasma buprenorphine level—either < 2 ng/mL or ≥ 2 ng/mL—measured immediately prior to randomization and the daily dose of buprenorphine.

From May 2022 through May 2023, 28 participants were randomized 2:1 CBD 600 mg:placebo; however, 6 of these participants did not receive any study drug.

Towards the end of enrollment of the first dose cohort, it became clear that financial constraints would preclude study of a higher dose cohort. In June 2023, randomization was reversed to 2:1 placebo:CBD to increase power by balancing the low CBD and placebo groups as much as was

possible in the remaining time. From June 2023 through January 2024, 7 participants were randomized 2:1 placebo:CBD 600 mg. This SAP is based on the study plan that includes these modifications. It is expected that there will be 21 patients in the 600-mg CBD arm ( $28*0.67+7*0.33$ ), and 14 patients in the placebo arm ( $28*0.33+7*0.67$ ).

### 3.2. Figure of Study Design

### 3.3. Schedule of Events

	Stabilize on BUP	BUP PK	Determine Eligibility	TREATMENT												Follow-up	
				0	1,2,4-6	3	7	8-13	14	15-20	21	22-27	28	29-31, 33	35,42,49,56		
Study day →	-14 to -7	-7	-7 to 0														
IC/IEC/Demogs				X													
MINI				X													
C-SSRS				X				X		X		X		X		X	
Randomization				X	X												
MedHx/PsychEval				X													
EKG				X										X			
Weight/Height					X									X			
Vitals (HR/BP)					X	X	X	X	X	X	X	X	X	X	X	X	X
AEs & ConMeds						X	X	X	X	X	X	X	X	X	X	X	X
Pregnancy Test				X	X	X	X	X	X	X	X	X	X	X	X		
Urine Drug Screen				X	X	X	X	X	X	X	X	X	X	X	X	X	X
Pulse Oximetry					X	X	X	X	X	X	X	X	X	X	X	X	
Lab Tests				X				X		X		X		X		X	X
Ovarian Function				X									X		X		
BUP Dosing	X	X	X	X	X	X	X	X	X	X	X	X	X	X	X	X	X
CBD Dosing						X	X	X	X	X	X	X	X	X	X		
PK Sample(s)		X		X		X	X		X			X		X		X	
Cue-induced cravings (DDQ)					X		X							X			
COWS					X	X	X	X	X	X	X	X	X	X	X	X	
PACS, STAI, PANAS, OAAS			X	OAAS/ only	X	X	X	X	X	X	X	X	X	X	X	X	X

### 3.4. Objectives and Endpoints

Objectives	Endpoints
Primary: To evaluate the safety and tolerability of CBD in the study population.	Primary: Number of treatment-emergent adverse events over the 28-day treatment period by study arm. Secondary: Changes in liver enzymes, pulse oximetry, sedation, and cardiovascular measures (heart rate, blood pressure, and cardiac rhythm and conduction on EKG).
Secondary: To determine the extent to which CBD (600 mg/day) reduces cue-induced craving for opioids relative to placebo.	Primary: Cue-induced craving for opioids, assessed using the Desires for Drug Questionnaire (DDQ)  in the context of an opioid cue-induction paradigm, assessed in the laboratory session before CBD dosing on Day 0 (baseline without CBD) and on Days 7 and 28 (after adjunctive treatment with CBD) Secondary: Spontaneous opioid craving, assessed using the Penn Alcohol-Craving Scale, as modified to assess opioid craving;  affect, assessed using the Positive and Negative Affect Schedule (PANAS),  Anxiety, assessed by state subscale of the Spielberger State-Trait Anxiety Inventory,  Percentage of patients with increase in their buprenorphine dose, Treatment retention, as indicated by number of days of continued participation
Exploratory: A. To evaluate effects of CBD on metabolism of other endocannabinoids, i.e., N-arachidonylethanolamide (anandamide) and 2-arachidonoyl-glycerol (2-AG) levels. B. To assess pharmacokinetics of CBD in patients receiving buprenorphine for treatment of OUD.	Plasma levels of anandamide and 2-AG. CBD pharmacokinetics—time to reach steady state and accumulation parameters (C max , AUC 0-24 ). In addition, the buprenorphine/norbuprenorphine ratio will be determined to evaluate potential drug-drug interactions of CBD with buprenorphine metabolism (dealkylation). Although this ratio does not, by itself, an increase in the ratio, concurrent with the emergence of hypoxia and/or sedation would be an AE.

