## 4.2. Handling of Missing Data

For the classification of Treatment emergent adverse event (TEAE) and concomitant medication, the following will be applied in the described order:

- a. If all dates/times (start and stop) are missing, the event/medication will automatically be classified as a TEAE/concomitant medication.
- b. For AEs with a missing start date/time, if the event end date/time is prior to first instillation, the event will not be classified as a TEAE.
- c. If only the AE start year/ medication end year is present and is the same or is after the first instillation year unit, the event/medication will be classified as a TEAE/concomitant medication.
- d. If the AE start month and year/medication end month and year are present and are the same or after the first instillation month and year units, the event/medication will be classified as a TEAE/concomitant medication.

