### **10.1. Adverse Events**

AEs related to study procedures will be collected from the signing of the ICF through the end of the study. An adverse event (AE) will be recorded if it is a new event that was not present at Screening or is the worsening of an event present at Screening.

All AEs included will be coded using MedDRA. All AE summaries will be restricted to TEAEs only. Summary tables will include the number of participants (%) experiencing an event and the number of events. Participants will be counted only once for each SOC and PT level (categorical descriptive analysis). When TEAEs are reported by relatedness and/or severity, each TEAE will be counted once per subject at the worst/highest level of the assessment (e.g., highest relationship to investigational device or greatest severity).

The MedDRA version used for reporting will be described in the relevant table and listing footnotes.

The TEAE summaries will include:

- Overall summaries of TEAEs.
- TEAE summaries by SOC and PT.

A comprehensive listing of all adverse events will be provided in a by-subject data listing.

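### The primary safety endpoint is a raw count of TEAEs in arms of unequal size with no rate per time at risk, and its 28-day window is not carried into the AE tables

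*SAP*

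**What the plan says.** **Endpoint and tables.** For the primary objective, SAP 3.4 lists "Primary: Number of treatment-emergent adverse events over the 28-day treatment period by study arm". SAP 10.1 describes the output: "Summary tables will include the number of participants (%) experiencing an event and the number of events". It also says "All AE summaries will be restricted to TEAEs only". It does not ask for a mean per participant, person-time or a rate. SAP 4.1 sets a denominator for percentages only and rules out inferential statistics for safety endpoints. AEs are analysed in the Safety population (SAP 5 and 10). Exposure is summarized separately, on the randomized population (SAP 9), with no link to AEs.

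**Arm sizes and time on study.** SAP 3.1 states "It is expected that there will be 21 patients in the 600-mg CBD arm", with 14 on placebo, and reports that 6 of the first 28 randomized received no study drug. Under Duration of Treatment and Dropout, the protocol withdraws participants who stop buprenorphine or methadone, or leave the center, before completing the 28 days.

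**Window.** SAP 3.1 labels the treatment period and what follows it as "primary data collection phase, and 4) a 28-day follow-up period after termination of treatment with study medication (secondary data collection phase". On recording it says "On each study day, vital signs were taken, and patients reported adverse events, which were monitored and recorded", and 10.1 adds "AEs related to study procedures will be collected from the signing of the ICF through the end of the study". The TEAE rules in SAP 4.2 refer only to a start. Under rule (d), for partial dates, where the known month and year "are the same or after the first instillation month and year units, the event/medication will be classified as a TEAE/concomitant medication". I read instillation as first dose.

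**The concern.** A raw number of events by arm reflects three things: the event rate, the number of people and how long they were observed. The arms are unequal by design history, and early leavers stop contributing time. A difference in counts can therefore appear when the rates are the same, or a real difference can be masked. Because safety is descriptive only, readers will judge the trial's primary objective from these figures without a model or interval to correct them.

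The window adds a smaller problem. A programmer working from 10.1 and 4.2 alone would have no instruction to stop at the end of treatment, so the table could take in off-drug events that 3.4 excludes.

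**Working it through.** **Inputs.** From the SAP: the allocation (28 participants at 2:1, 7 at 1:2), 6 undosed among the first 28, and the 28-day window. Assumed, because the documents give no figures: weekly AE rates, mean weeks at risk, on-drug and off-drug rate ratios, and the volume of follow-up events.

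**1. The plan's own figure.** 28 × 0.67 + 7 × 0.33 = 21.07 and 28 × 0.33 + 7 × 0.67 = 13.93. The stated 21 and 14 reproduce.

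**2. Arm size alone.** With equal rates and equal time, the count ratio is the ratio of arm sizes.
- As randomized: 21/14 = 1.50.
- Dosed, if the six split 4:2 and all seven later participants were dosed: (21 − 4)/(14 − 2) = 17/12 = 1.42.
- Extremes, if all six came from one arm: 15/14 = 1.07 or 21/8 = 2.63.

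**3. Time at risk and the percentage.** Take equal weekly rates, Poisson events, and give everyone in an arm that arm's mean time. The percentage with at least one event is 1 − exp(−rate × weeks).

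| Rate per week | 4 weeks | 3 weeks | Gap (points) |
|---|---|---|---|
| 0.10 | 33.0% | 25.9% | 7.1 |
| 0.25 | 63.2% | 52.8% | 10.4 |
| 0.50 | 86.5% | 77.7% | 8.8 |

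**4. Time at risk and the count**, at 0.25 per week and 21:14.
- Longer on CBD: 21 × 4 × 0.25 = 21.0 against 14 × 3 × 0.25 = 10.5, ratio 2.0.
- Longer on placebo: 21 × 3 × 0.25 = 15.75 against 14 × 4 × 0.25 = 14.0, ratio 1.13.
- Dividing by arm size leaves 4/3 = 1.33 or 3/4 = 0.75.
- Dividing by participant-weeks gives 21.0/84 = 0.25 and 10.5/42 = 0.25, ratio 1.0. The reversed case also gives 1.0 (15.75/63 and 14.0/56).

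**5. Window.** Let the on-drug ratio be 2, let f be recorded follow-up events as a share of placebo on-treatment events, and let c be the off-drug ratio. The pooled ratio is (2 + c × f)/(1 + f).

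| | f = 0.25 | f = 0.50 | f = 1.00 |
|---|---|---|---|
| c = 1 (no off-drug effect) | 1.80 | 1.67 | 1.50 |
| c = 1.5 | 1.90 | 1.83 | 1.75 |
| c = 2 (full carry-over) | 2.00 | 2.00 | 2.00 |

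**The case against.** **The window is already fixed.** SAP 3.4 limits the endpoint to 28 days, 3.1 labels follow-up as secondary, and 10.1 is a generic list of outputs that does not redefine the endpoint. A rule for partial dates needs only a start boundary to do its job. The collection sentence in 10.1 literally concerns procedure-related AEs. Most of this stands, so the window is a secondary point: a stated limit that was not carried through. The by-subject listing would let a reader separate the periods, but the summary table should do so itself.

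**The denominator is largely handled.** The percentage is reported beside the count, and anyone can divide a count by the arm size. That answers the arm-size part for an attentive reader. It does not answer time at risk, as step 4 shows. SAP 4.1's general rule for continuous variables could yield a mean per participant, but 10.1 does not ask for one, and it would have the same limit.

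**The sizes are hypothetical.** This stands. The withdrawal rule is the same in both arms, the trial is randomized and double-blind, and the example of 4 against 3 weeks is a large imbalance. With equal mean time the gap in step 3 is zero. However, SAP 3.4 makes days of continued participation an outcome to be compared between arms, so the plan itself does not take equal time for granted.

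**Conclusion.** The concern holds as an inexpensive improvement to the primary safety summary. Equal per-person rates would give a raw count ratio of about 1.4 to 1.5. The lower figure assumes a 4:2 split of the six undosed and that all later participants were dosed. The planned percentage removes the arm-size effect but not an imbalance in time at risk. Under the assumed rates and 4 against 3 weeks, 7 to 10 points can arise with no true difference.

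Three stronger readings are not supported:
- A reader might infer that the primary safety result covers 56 days or has no window. SAP 3.4 states 28 days; what is missing is an end boundary in the TEAE rules and its repetition in 10.1.
- A reader might infer that pooling follow-up must hide a drug effect. It dilutes an assumed ratio of 2 to between 1.8 and 1.5 only with no off-drug effect; with full carry-over the ratio does not change.
- A reader might count follow-up contact days from the Schedule of Events to size the dilution. In the text available for this review, its marks and day labels do not align, so no figure is taken from it. The case for follow-up recording rests on SAP 3.1 and 10.1.

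Nothing here shows that the arms did differ in time at risk. No alpha or power is affected.

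**What to change.** 1. In SAP 10.1, beside the event count and n (%), report TEAEs per participant-week at risk by arm in the Safety population. Count time from first dose to the earlier of withdrawal or the end of the 28-day treatment period, and show total participant-weeks. Keep it descriptive, in line with SAP 4.1.
2. In SAP 10.1, give TEAEs an end boundary. Base the primary table on onset from first dose to the end of the 28-day treatment period, and tabulate follow-up events separately.

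The cost is some SAP wording, one column and one extra table, from AE, dosing and participation data already collected. The downside is smaller cells once events are split by period. A weekly rate also corrects fully only if events occur at a roughly constant rate. If they cluster early, an arm with more early leavers will show a higher rate, which is why the counts and percentages should stay alongside it.

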### 3.5. Sample Size

Sample size is based on the change in cue-induced craving from baseline to 28-days, the end of the acute treatment period. The actual number of subjects enrolled has changed since the initial protocol. This section will focus on the standardized effect size needed to show 1-sided significance level of  $\alpha = 0.025$  (equivalent to  $\alpha = 0.05$  two sided but reflecting our directional hypothesis), based on 21 treated and 14 placebo subjects. Based on the SAS power calculation below, if there is a standardized effect size of  $d = 1.0$ , then there is a power of 0.80.

```
proc power;  
  twosamplemeans test=diff  
  groupmeans = 0 | 1  
  stddev = 1
```

```
groupweights = (14 21)
ntotal = 35
power =. ;
run;
```

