## **5. Analysis Populations (Analysis Sets)**

The randomized population will include all subjects randomized regardless of whether they had any study drug.

The safety population will include all subjects who received at least one treatment of study drug and will be used for the summaries of all baseline, demographic, and safety data.

The full analysis set (FAS) population is a subset of safety population and consists of those that have at least one post-baseline efficacy measurement. This population will be used for the summaries of all efficacy data.

The pharmacokinetic (PK) population is a subset of the safety population and consists of those who have at least one PK assessment.

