# **11. Efficacy**

All efficacy analyses will be based on the Full Analysis Set Population and Efficacy endpoints will be summarized descriptively. Absolute change and percent change will be reported for all efficacy endpoints. All efficacy data will be provided in listings.

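### The stated power of 0.80 counts all 35 randomised participants, but at most 29 can enter the Full Analysis Set; power at d = 1.0 is then about 0.72 and cannot exceed 0.74

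*SAP*

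**What the plan says.** SAP Section 3.5 bases the sample size on the change in cue-induced craving from baseline to Day 28. It works "based on 21 treated and 14 placebo subjects. Based on the SAS power calculation below" and concludes that, for a standardised effect of 1.0, "then there is a power of 0.80". The code has a total of 35, weights of 14 and 21, a standard deviation of 1 and "groupmeans = 0 | 1".

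Four other statements bear on this figure:

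- Section 3.1 obtains 21 and 14 as the expected split of everyone randomised, 28 under one ratio and 7 under the reversed ratio.
- Section 3.1 also reports that "28 participants were randomized 2:1 CBD 600 mg:placebo; however, 6 of these participants did not receive any study drug".
- Section 5 limits the safety population to those who had at least one dose. It says that the FAS "is a subset of safety population and consists of those that have at least one post-baseline efficacy measurement".
- Section 11 says: "All efficacy analyses will be based on the Full Analysis Set Population".

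Section 3.5 makes no allowance for the undosed participants or for later loss.

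**The concern.** The power calculation and the efficacy analysis use different populations. Section 3.5 counts participants as randomised; Section 11 analyses participants who were dosed and then measured. The 6 undosed are not a forecast of dropout. They are a recorded fact, reported in the same SAP, and its definitions exclude them from the efficacy analysis.

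Cue-induced craving is the SAP's primary efficacy target and the subject of its only power statement. If the craving result is null, readers will judge it against a stated 20% chance of missing a true effect of 1.0, when the planned analysis carries a chance of at least 26%.

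**Working it through.** **Inputs**

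- Effect 1.0 and SD 1: code in Section 3.5.
- Significance level: the text gives the effect "needed to show 1-sided significance level of" 0.025, described as equivalent to 0.05 "two sided but reflecting our directional hypothesis". The code sets no sidedness, so it runs two-sided at 0.05. Both versions give 0.803 at 21/14, so sidedness is not the issue.
- Arms as randomised: 28 × 2/3 + 7 × 1/3 = 21 CBD and 28 × 1/3 + 7 × 2/3 = 14 placebo (Section 3.1).
- Never dosed: 6 of the first 28 (Section 3.1); their arms are not given.

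**Method.** Pooled two-sample t-test with the noncentral t distribution, which is what the SAP's procedure computes:

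- noncentrality = d × √(n₁n₂ / (n₁ + n₂)), with n₁ + n₂ − 2 degrees of freedom;
- power = probability that a noncentral t variable lies beyond the two-sided 5% critical value.

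**Step 1: reproduce the stated figure.** For 21/14, noncentrality = √(21 × 14 / 35) = √8.4 = 2.898, with 33 degrees of freedom and critical value 2.035. Power = 0.803, which matches 0.80. The method is sound; the question is the number put into it.

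**Step 2: ceiling on the FAS.** 35 − 6 = 29.

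**Step 3: expected split of the 29.** Assume that the 6 were lost in the 2:1 ratio under which they were randomised (4 CBD, 2 placebo). Then 21 − 4 = 17 and 14 − 2 = 12. Noncentrality = √(17 × 12 / 29) = √7.034 = 2.652, with 27 degrees of freedom and critical value 2.052. Power = 0.725. Keeping the 21:14 proportion instead (17.4/11.6) gives 0.720.

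**Step 4: every split of the 6, starting from 21/14**

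| Undosed from CBD | CBD / placebo | Power at d = 1.0 |
|---|---|---|
| 0 | 21 / 8 | 0.641 |
| 1 | 20 / 9 | 0.671 |
| 2 | 19 / 10 | 0.694 |
| 3 | 18 / 11 | 0.712 |
| 4 | 17 / 12 | 0.725 |
| 5 | 16 / 13 | 0.733 |
| 6 | 15 / 14 | 0.737 |

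A 15/14 split is the most even division of 29, so 0.737 is a ceiling whatever the arms of the 6 or the realised randomisation. The chance of missing a true effect of 1.0 is at least 1 − 0.737 = 0.263.

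**Step 5: effect needed for 80% power.** 0.996 at 21/14, 1.096 at 17/12, 1.080 at 15/14 and 1.207 at 21/8.

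**Step 6: why 29 is an upper limit.** FAS entry also needs a post-baseline efficacy measurement, and Section 3.1 does not say whether any of the last 7 went undosed. The primary efficacy estimate is at Day 28, and the protocol (Duration of Treatment and Dropout) withdraws participants who stop buprenorphine or methadone or leave the centre early. The documents give no rate of loss. Assuming 10%, 20% or 30% proportional loss from 17/12, with those lost contributing nothing, power is 0.68, 0.62 or 0.56.

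**The case against.** The strongest reply is that correcting Section 3.5 changes nothing that will be done. By the SAP's account the last participants were randomised by January 2024, so the power figure no longer drives enrolment, and the population, endpoint and model all stay the same. Craving belongs to the secondary objective, and SAP Section 2 calls the efficacy information preliminary. Section 11 requires 95% confidence intervals for the treatment difference, and Section 6 requires the size of each population. A reader will therefore see the real precision. The calculation is also correct for the 35 that it declares.

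Much of this is fair. The consequence lies in how the result is read, not in how the trial runs, and the confidence intervals limit the harm. But Section 3.5 was written for the changed enrolment and says that it concentrates on the effect size needed. That effect size is the figure that is too small, and the undosed participants were already known.

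Two points of precision also stand. The value 0.725 depends on an assumed split of the 6, so it should be given with its range. The loss figures in Step 6 rest on assumed rates and on a t-test, whereas the planned repeated-measures model would take some information from participants seen only on Day 7. The SAP gives no correlation from which to compute that gain, so these figures are illustrative and probably somewhat pessimistic. Neither point rescues 0.80, because no model can recover participants who are outside the FAS.

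**Conclusion.** The concern holds. The 0.80 is the right answer for 35 participants, but the SAP's own statements limit the efficacy analysis to 29. At d = 1.0, power is about 0.72 if the 6 undosed followed the allocation ratio. Across splits from the expected 21/14 it runs from 0.64 to 0.74, and it cannot exceed 0.74 for any division of 29. The effect needed for 80% power is about 1.10 at 17/12, against the stated 1.0.

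The ceiling of 29 rests only on the documents. The central value rests on the 2:1 assumption, and the lower end of the range on the expected 21/14. All the figures use the SAP's two-sample t-test; power under the repeated-measures model may differ slightly. The statement should be corrected because the planned analysis cannot have the power it claims.

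**What to change.** Rewrite SAP Section 3.5 on the analysis population:

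- State that at most 29 participants can enter the FAS, with an expected 17 on CBD and 12 on placebo if the 6 undosed followed the 2:1 allocation.
- Report power at d = 1.0 as about 0.72 (range 0.64 to 0.74 over the possible splits), and the effect needed for 80% power as about 1.1.
- Add a line giving power at the number expected to have a Day 28 DDQ score, with the assumed loss stated.

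The cost is one rerun of the power procedure and a few sentences, and the figure becomes less favourable. No extra enrolment and no change to the endpoint, population or model is needed.
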